16.3 REPORTING PROCEDURES AND TIMELINES

16.3.1 Documentation

Device deficiencies (DD) and all adverse events (AE) including all serious adverse events (SAE) are collected, fully investigated and documented in the source document and appropriate case report form (CRF) during the entire investigation period, i.e. from the operating room when the initial incision(s)

CONFIDENTIAL

is made to start the implantation procedure until the last CIP specific procedure, including a safety follow-up period.

- Documentation of AEs (including SAEs) by the PI includes diagnosis or symptoms, start and stop dates of event, event treatment, event resolution, assessment of severity, seriousness and causal relationship to device and/or investigation procedure.
- Documentation of DDs by the PI includes description of event, start date, investigational device information, action taken with regard to the investigational device, and whether the DD led to an AE. The Sponsor shall review all DDs and determine and document in writing.

The investigator will follow each subject who experiences an AE until the event resolves, resolves with sequelae, or no further improvement is expected. In the unusual circumstance that an AE has not resolved by the time of the subject's completion of the study, an explanation will be entered

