5.1 RISKS

The potential risks for subjects enrolled in the trial include those related to surgery, lumbar spine surgery, interspinous spacers (including the Lobster device and other interspinous spacers) and instrumentation, or imaging for the study that are not standard of care. There is always a chance that unforeseen risks may occur.

Risks generally associated with any surgery include:

- Anesthetic medication reactions
- Surgery at the incorrect location, side or level
- Blood loss, blood vessel damage, phlebitis or hematoma
- Blood transfusion which may cause circulatory collapse, blood incompatibility, kidney damage, hepatitis, infection with HIV
- Myocardial infarction or circulatory problems
- Deep vein thrombosis, pulmonary embolism or thrombus formation in other vessels
- Stroke
- Fever or infection

CONFIDENTIAL

Page **30** of **67**

- Pneumonia
- Injury to muscle, soft tissues or nerves
- Wound swelling, draining or delayed healing
- Discomfort and rehabilitation associated with recovery from surgery
- Inability to perform certain tasks, such as lifting, exercising etc.
- Death

Risks associated with lumbar spine surgery include:

- Damage to nerve roots or the spinal cord causing partial or complete sensory or motor loss (paralysis)
- Loss of bladder and/ or bowel functions
- Dural leaks (tears in the tissue surrounding and protecting the spinal cord)
- Instruments used during surgery may break or malfunction which may cause damage to the operative site or adjacent structures
- Fracture, damage or remodeling of adjacent anatomy, including bony structures or soft tissues during or after surgery
- New or worsened back or leg pain

Risks associated with lumbar spine implants (including the Lobster and other interspinous spacers) and associated instruments include:

- Sensitivity or allergy to the implant material
- Failure of the device/ procedure to improve symptoms and/ or function
- Pain and discomfort associated with the operative site or presence of implants
- Implant malposition or incorrect orientation
- Spinous process fracture
- Wear debris which may damage surrounding soft tissues including muscle or nerve
- Scar tissue may form at implant site
- Migration or dislodgement of the implant from the original position so that it becomes ineffective or causes damage to adjacent bone or soft tissues including nerves

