8.4.3 Subject Identification

Subjects who consent to participate shall be assigned a unique Subject Identification Number to deidentify their information. This Subject Identification Number will be captured on the Screening & Enrollment Log and used to identify them on all source documents and eCRFs thereafter.

A record of all screened subjects will be maintained in a Screening/Enrollment Log. The date of screening, results of screening (included or not) and, if not eligible, the primary reason for excluding the subject, enrollment status (enrolled or not) and, if not enrolled, the primary reason will be recorded.

Please note, for purposes of the study population a subject is considered enrolled at the time of surgical incision.

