16. SAFETY REPORTING

16.1 DEFINITION AND ASSESSMENT OF (SERIOUS) ADVERSE EVENTS AND OTHER SAFETY RELATED EVENTS

AEs/DDs will be reported according to MDR Regulation (EU) 2017/745 and ISO 14155:2020, while recognizing and following other specific laws, regulations, directives, standards and/or guidelines, as appropriate, as required by the country(ies) in which the study is conducted.

The list of foreseeable AEs and anticipated adverse device effects, together with their likely incidence, mitigation or treatment are detailed in the Investigator Brochure (IB) and IFU of the medical device used in this study.

As detailed in the CIP, events of the following types are captured for all subjects throughout the study, between the start time of enrolment and the end of subject participation (i.e., completion of the study or withdrawal of consent).

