16.1.2 Adverse Event (AE)

Any untoward medical occurrence, unintended disease or injury or any untoward clinical signs, including an abnormal laboratory finding, in subjects, users or other persons, in the context of a clinical investigation, whether or not related to the investigational device. (MDR Article 2(57))

Note: Pre-Existing Medical Conditions; any medical conditions (including planned surgeries and planned hospitalizations) present at enrolment, which do not worsen in duration, severity or frequency during the study **are not adverse events (AE)**. These pre-existing medical conditions should be adequately documented in the patient's medical history in the eCRF. Medical conditions present at enrolment which worsen after exposure to study treatment will be recorded as an AE on the Adverse Event Form of the eCRF.

At each evaluation, patients should be interviewed in a non-directed manner to elicit potential AEs from the patient. The occurrence of an AE will be based on changes in the patient's physical

examination, laboratory results, and/or signs and symptoms at a clinical visit, otherwise based on information given by the patient over the telephone.

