19. STATISTICAL METHODS

19.1 ANALYSIS SETS

The analysis data sets will be defined in a way that mirrors the Superion P140004 study.

The primary analysis cohort for this study will be the Modified Intent-to-Treat Cohort, defined as: Modified Intent-to-treat patient population (mITT): The mITT patient population will include all patients having an anesthesia start time. Subjects with an anesthesia start time but that do not receive the device will be failures.

Confirmatory analysis will be performed in the Per Protocol Cohort, defined as: Per protocol (PP) Population: The PP patient population will include all subjects with 12-month follow-up data and no major protocol deviations and subjects that failed before 12 months

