19.4 SAFETY ANALYSES

Assessment of the safety of the investigational implant will include an evaluation of the incidence and severity of complications and adverse reactions associated with the treatment. Adverse event rates will be summarized by type of AE and for specific AEs in two ways: 1) per patient incidence of specific AEs and classes of AEs and 2) by event, summarizing event counts by visit interval over time and in accordance with FDA Guidance. Device and procedure-related events will be summarized by severity and relatedness. Events listings that include details such as relatedness, severity, onset and resolution status will be provided for all events and relevant subsets of events such as serious events and related events. Primary safety comparisons will be performed using the mITT analysis set. The summary tables will show the adverse events (in coded terms), the total number of events, and the number and the percentage of subjects affected in each treatment group ("subject wise evaluation") and stratified by relation to device and severity.

CONFIDENTIAL Page 60 of 67 The event rates observed in the Superion SSED (P140004) will be used as clinical guideposts only. There is no formal statistical hypothesis test on these endpoints. Please note that the primary endpoint captures both safety and effectiveness, and therefore these events are considered interesting but appropriately evaluated in this framework. Additional details regarding the safety comparisons will be provided in the SAP.

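### Adverse-event collection opens at incision, but subjects enter the safety analysis set at anaesthesia start, so the interval between the two is not covered

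*Protocol*

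**What the plan says.** **Collection window.** Section 16.3.1 collects device deficiencies and all adverse events, serious ones included, "from the operating room when the initial incision(s" and, continuing over a page break, "is made to start the implantation procedure until the last CIP specific procedure, including a safety follow-up period". Section 16.1 describes capture "between the start time of enrolment and the end of subject participation". Section 8.4.3 states that "a subject is considered enrolled at the time of surgical incision", and Sections 8.4.2 and 10.1 define enrolment in the same way.

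**Safety denominator.** Section 19.1 says: "The mITT patient population will include all patients having an anesthesia start time". It adds that anaesthetised subjects who do not receive the device count as failures. Section 19.4 says: "Primary safety comparisons will be performed using the mITT analysis set".

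**Related text.** Section 5.1 puts "Anesthetic medication reactions" at the head of its list of general surgical risks. Section 16.1.2 does not treat as adverse events those medical conditions "present at enrolment, which do not worsen in duration, severity or frequency during the study". Section 10.3 records the times of first incision and skin closure on Day 0 and does not mention the anaesthesia start time.

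**The concern.** An incidence needs a numerator and a denominator that cover the same period. Here a subject joins the denominator at anaesthesia start, while events are collected only from incision. The interval between the two is when a reaction to sedation or to an anaesthetic drug may well first appear, and the protocol names that risk itself.

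Two things are at stake. First, the adverse-event and procedure-related summaries in Section 19.4 could be understated, and never overstated. The study has a single arm and sets its event rates beside published rates for an approved spacer as guideposts, so an understatement favours the device. Second, the classification in Section 16.2.3 and the reporting duties in Sections 16.3.2 and 16.3.3 act on recorded events. A serious event before incision has no clear way into them. An analysis plan written later cannot recover events that the protocol did not ask sites to collect.

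**Working it through.** The plan gives no figure to reproduce, so the check is to set the passages in time order.

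1. **Anaesthesia start.** The subject enters the mITT set (Section 19.1) and therefore the safety set (Section 19.4).
2. **Incision.** The subject is enrolled (Sections 8.4.2, 8.4.3 and 10.1), and adverse-event collection opens. The two statements of the window agree: Section 16.3.1 names incision directly, and Section 16.1 names enrolment, which is incision.
3. **Between 1 and 2.** The subject is in the denominator and outside the window.

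Three cases follow from a literal reading.

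- *Reaction resolved before incision, procedure continues.* It began and ended before the window opened. Nothing in Sections 16.1 or 16.3.1 calls for it to be recorded.
- *Reaction still present at incision.* Its onset is before the window. Whether it is recorded depends on how a site reads the note on pre-existing conditions in Section 16.1.2.
- *Procedure abandoned before incision.* The subject is never enrolled, so no collection period exists. Under Section 19.1 the same subject is an mITT failure. Under Section 8.5 the subject may also be logged as a screen failure.

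I then looked for text that sets an earlier start. The Day 0 list in Section 10.3 includes a review of adverse events ahead of the surgical steps, but gives no start time for it. The same list contains the CT scan that confirms device placement, so it is not a list of pre-incision tasks. Table 10-1 marks adverse-event recording for the index procedure and leaves it blank for screening, again with no start time within the day. Neither displaces the explicit windows in Sections 16.1 and 16.3.1.

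**Size.** The protocol gives neither the number of subjects expected to be anaesthetised but not incised nor a rate of pre-incision reactions. Taking planned enrolment as an approximate denominator (191 minimum, 250 maximum, Section 19.3), one unrecorded subject would change a per-patient adverse-event rate by 1/191 = 0.52 to 1/250 = 0.40 percentage points. That converts one subject into a rate. It does not estimate the undercount.

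**The case against.** The strongest reply is that the mismatch has little consequence. Much of that reply stands.

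- **Primary safety.** A reader might infer that the primary safety rate is biased by every missed reaction. The documents do not support this. Section 7.4 names device integrity failure, neurological deficit at the index level, spinous process fracture, deep infection, death and permanent device-attributed disability. Anaesthetic reactions are not named. Before incision no device is in place, so realistically only death, or rarely a neurological deficit, could arise. The list is introduced as non-exhaustive, which leaves a little room but no more.
- **No test depends on it.** Section 19.4 has no formal safety hypothesis, and a subject without a device is already an effectiveness failure under Section 19.1. Both points are correct. The concern is with descriptive summaries and with reporting.
- **Pre-existing conditions.** A reader might infer that Section 16.1.2 turns a pre-incision reaction into medical history. That is an inference. The note concerns medical conditions, including planned surgery and hospitalisation, to be documented as history. It cannot cover a reaction that resolved before incision, and a condition that worsens after exposure is recorded. The definition of an adverse event in the same section is broad.
- **Practice on the day.** With adverse-event entries on Day 0 both in the opening list and after surgery, a careful site may record such an event anyway. Section 8.5 also asks for surgery-visit data before incision and for a reason for exclusion. It would therefore be too strong to say that these events are certainly lost. But a logged reason for exclusion is not an adverse-event record, Section 8.5 allows those data to be incomplete, and sites that read the rule differently would report differently.

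**Conclusion.** The mismatch stands as a matter of text: the collection window opens at incision and the safety set opens at anaesthesia start. Followed as written, the protocol leaves a named procedural risk outside the numerator for subjects who are in the denominator. The error can run in one direction only, towards lower rates, and it affects the general and procedure-related summaries of Section 19.4.

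Its size cannot be computed from the protocol and is probably small. A reader might be tempted to assume a handful of missed subjects and quote a loss in percentage points, but no count in the document supports such a figure. The conclusion assumes that anaesthesia starts before incision and that sites follow the stated windows rather than the looser Day 0 entries. It does not extend to the tested effectiveness endpoint, and it reaches the named primary-safety complications only in rare cases such as death.

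**What to change.** In Sections 16.1 and 16.3.1, start the recording of adverse events no later than anaesthesia start, so that the window opens no later than entry into the safety set. In Section 16.1.2, state that a condition is judged pre-existing at that same time. Make sure the anaesthesia start time, which defines the mITT set, is captured on Day 0. Section 10.3 does not list it, though the case report form is not shown and may already hold it.

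The cost is wording in three sections, at most one additional Day 0 field, and a few more recorded events. Sample size and the effectiveness analysis are unchanged. The edit should be in place before subjects are treated, because events not collected on the day cannot be recovered reliably afterwards.

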16.3.2 Reporting of Safety related events to Sponsor

Any SAE/ADE/SADE/USADE/DD (including serious public health threat) must be recorded correctly in the electronic Case Report Form (eCRF) immediately, but no later than within 3 calendar days (CDs)/24h for serious public health threat after the investigation site study personnel has become aware of its occurrence even if not all the information is available. Other than reportable events should be reported within 30 calendar days after the investigation site study personnel's awareness of the event.

Type of Event	Timeline for Reporting
ADE	Immediately but in any event no later than 3 CDs
SAE	Immediately but in any event no later than 3 CDs
SADE	Immediately but in any event no later than 3 CDs
USADE	Immediately but in any event no later than 3 CDs
All other AEs	In a timely manner, usually within 30 CDs
Device Deficiency	Immediately but in any event no later than 3 CDs
Serious Public Health threat	Immediately but in any event no later than 24 hours

Table 16-1. Timelines for events reporting by Investigators to the Sponsor

Emergency Contact details for Adverse Events/Device Deficiencies/Serious health threat reporting: Sponsor: [name] Quality Manager Diametros Medical srl [name] [contact]

[name]

[Diametros Medical, LB2CT]

16.3.3 Reporting of Safety related events to Ethics Committee

The Sponsor or designee reports to the IEC promptly any SAE which has a causal relation with the device, comparator, or procedure/test method or where a causal relation appears to be possible.

In order to ensure prompt notification, the Sponsor may initially submit an incomplete notification.

If safety and health hazards that require measures must be taken immediately during the conduct of the investigation, the Sponsor notifies the IEC within 2 days of these measures and the circumstances which made them necessary.

16.3.4 Periodic Safety Reporting

An Annual Safety Report (ASR) is submitted by the Sponsor to the IEC, yearly. The ASR contains a list of all SADEs and DDs and a report on their degree of seriousness, causal relationship with the device and procedure and on subjects' safety.

16.3.5 Other reporting

Other reporting is done according to provisions of MD vigilance as per Art. 87-90 MDR.

16.3.6 Pregnancy Reporting

In order to ensure the safety of subjects who may become pregnant during the course of the study, subjects will be asked to return for all protocol-specified visits and will undergo all protocol-specified assessments at each follow-up visit, unless contraindicated, until the successful completion of the 24-month follow-up visit.

The Investigator will continue to follow the subject to report the outcome of the pregnancy to the Sponsor (i.e. live birth (full term or preterm birth), stillbirth, spontaneous abortion, and induced abortion.

16.4 TREATMENT OF AES

The Investigator will treat all subjects who experience an adverse event related to the device until the adverse event is resolved, resolved with sequelae, or no further improvement is expected. For all other adverse events, adverse event treatment and physician follow up will be dictated by standard of care.

16.5 SECONDARY SURGICAL INTERVENTIONS (SSIs)

The occurrence of the following SSIs will be documented for this study:

A **revision** is a procedure that adjusts or in any way modifies or removes part of the original implant configuration, with or without replacement of a component. A revision may also include adjusting the position of the original configuration.

A **removal** is a procedure where all of the original system configuration are removed with or without replacement.

[Diametros Medical, LB2CT]

CONFIDENTIAL Page 56 of 67 A **reoperation** is any surgical procedure at the involved level(s) that does not removal, modification, or addition of any components to the system.

A **supplemental fixation** is a procedure in which additional instrumentation not under study in the protocol is implanted (e.g., supplemental placement of a rod/screw system or a plate/screw system).

16.6 SAFETY OVERSIGHT: CLINICAL EVENTS COMMITTEE (CEC)

A clinical event committee (CEC) will be established. The CEC is an independent committee consisting of three (3) spine surgeons with pertinent expertise who are not participants in the study and who do not have any other real or potential conflicts of interest. The CEC will meet periodically to review all adverse events, protocol deviations, SSIs, and neurological deterioration.

17. CLINICAL MONITORING

17.1 SITE MONITORING

The study will be monitored to ensure that it is conducted in conformance with the monitoring plan by the Sponsor to assess continued compliance with the protocol and to ensure and to ensure that applicable regulations and standards are followed. In addition, the monitor verifies that study records are adequately maintained, that data are reported in a satisfactory manner with respect to timeliness, adequacy, and accuracy, and that the Investigator continues to have sufficient staff and facilities to conduct the study safely and effectively.

The study may also be subject to a quality assurance audit by the Sponsor or its designees, as well as inspection by appropriate regulatory authorities. It is important that the Investigator and relevant study personnel are available during on-site monitoring visits or audits and that sufficient time is devoted to the process.

The organization responsible for monitoring the study is:

[name] General Manager Email: [contact] [contact]

In addition to ensuring adequate communication between the Investigators and the Sponsor, the monitor's duties include on-site visits and review of study documents and reported data. The Monitor will be provided with appropriate device and protocol training prior to the study and will follow a Monitoring Plan for all study-related monitoring activities.

17.2 MONITORING ACTIVITIES

Monitoring visits include a pre-study Site Initiation Visit, periodic Interim Monitoring Visits, and a Close-Out Visit at the end of the site's participation in the study. The exact details of whether visits will be conducted on site or remotely shall be determined on an individual site basis as detailed in the Clinical Monitoring Plan,

Each site's Investigator will allocate adequate time for monitoring activities. The Investigator will also ensure that the monitor or other compliance or quality assurance reviewer is given access to the

study-related documents and study-related facilities and has adequate space to conduct the monitoring visit.

Monitoring visits will be documented on monitoring visit reports, and will aim to verify that:

- Compliance with the clinical protocol and applicable regulations is being maintained
- Source data is verified and signed-off upon as accurate
- Subject files are accurate and complete
- Subject withdrawal has been documented (if applicable)
- Subject non-compliance has been documented (if applicable)
- The Investigator and site staff are informed and knowledgeable of all relevant document updates concerning the clinical investigation
- Only authorized individuals are performing study-related functions
- The investigational device is being used according to the protocol and instructions for use
- Adequacy of staffing and facilities
- Signed and dated ICFs have been obtained from each subject
- eCRFs and queries are complete
- All adverse events and device deficiencies are reported to the Sponsor and the EC, as applicable
- All other required EC reports, notifications, applications, submissions, and correspondence are maintained in the Investigator's files and are accurate
- Corrective and preventive actions have been implemented (if applicable)

Monitoring activities related to eCRF, collected data, and reporting of adverse events will be done remotely through Smart-Trial software.

